**Figure 1: Safety Lead-in Study Design**

[figure not shown]

1. As assessed by site review

**Part 1:**

Part 1 of the study is designed as double-blind, randomized, placebo controlled study to assess the efficacy and safety of varlitinib plus capecitabine in comparison with placebo plus capecitabine in approximately 120 subjects (Figure 2). Eligible subjects will be randomized to varlitinib or placebo (BID, every day), each in combination with capecitabine (administered BID every day for 14 days, followed by a 7 day rest period). Treatment will continue until disease progression or development of toxicity or consent withdrawal or death. A DSMB will meet at a selected time point (to be confirmed) during Part 1 for review of safety data.

**Figure 2: Part 1 Study Design**

[figure not shown]

1. As assessed by site review
2. As assessed by Independent Central Review
3. Tumor response will be assessed every 6 weeks until disease progression
4. Following disease progression, patients in Part 1 will be followed for survival every 12 weeks until the DC0 for the primary analysis of Part 2
5. An additional DSMB review on safety data will be performed during Part 1, as described in DSMB charter

**Part 2:**

Part 2 of the study is designed as double-blind, randomized, placebo controlled study to confirm the efficacy of varlitinib plus capecitabine compared to capecitabine in approximately 350 subjects (Figure 3). Part 2 will follow the same design and treatment schedule as Part 1. This part of the study will commence following review of Part 1 results and will be independently powered.

**Figure 3: Part 2 Study Design**

## 2.2 Methods of Assigning Subjects to Treatment Groups

### Safety Lead-in:

This is a non-randomized single arm design. All eligible subjects will receive varlitinib 300 mg twice daily, every day plus capecitabine 1000mg/m^2 twice daily, Day 1 to 14, followed by a 7-day rest period (21 day cycle).

Each subject's eligibility will be reviewed by medical monitor during screening period, subjects will be sequentially enrolled after being screened for eligibility and providing consent.

In the case of discontinuation of chemotherapy owing to toxic effects, varlitinib or placebo therapy will be continued until disease progression, the development of unacceptable toxic effects, withdrawal of consent or death.

At screening, potential subjects will be assigned a unique screening number that starts with "S" and 4 digits (i.e. S1001) by electronic data capture system.

### Parts 1 and 2

At the initial screening visit, the investigator or suitably trained delegate will:

1. Obtain signed informed consent (main study) from the potential subject before any study specific procedures are performed.

2. Potential subjects will be assigned a unique screening number that starts with “S” and 4 digits (i.e. S1001) by electronic data capture system. This screening number will be sequential from safety lead in, and will not be repeated.
3. Determine subject eligibility in accordance with the protocol. Once the subject is confirmed to be eligible, the PI or suitably trained delegate will:
4. Assign eligible subject a unique randomization number via Randomization and Trial Supply Management (RTSM) system. Randomization numbers will start with “R” followed by 4 digits (i.e., R1001) and will be assigned strictly sequentially by RTMS (starting at R1001 for Part 1 and R2001 for Part 2), as subjects are eligible for randomization. This number is the subject’s unique identifier and is used to identify the subject with the assigned treatment. This randomization number will be available to the investigator in electronic data capture system.

### 2.2.1 Procedures for Randomization

Subjects must not be randomized unless all eligibility criteria have been met.

Subjects who satisfy all the entry criteria will be centrally assigned to study treatment by the RTSM, according to the randomization scheme generated by the CRO. Subjects will be randomized in a 1:1 ratio to either varlitinib or placebo, both on a background of capecitabine. The random scheme will be stratified by the following two covariates:

- Geographical region - US or Rest of World (ROW)
- Primary tumor location – Gall bladder (GB) or non-GB

The actual treatment given to subjects will be determined by the randomization scheme in RTSM. The randomization scheme will be produced using SAS® version 9.4, which incorporates a standard procedure for generating randomization numbers. One randomization list will be produced containing sufficient random numbers for each of the four randomization strata. A blocked randomization will be generated and all centers will use the same list in order to minimize any imbalance in the number of subjects assigned to each treatment group.

The dose and regimen of randomized therapy to be administered is as follows:

- Varlitinib 300 mg twice daily, every day
- Placebo twice daily, every day

Subjects in both arms will receive background chemotherapy with capecitabine 1000 mg/m^2 twice daily, Day 1 to 14, followed by a 7-day rest period (21 day cycle).

Subjects will be identified to the Centralized Randomization Center using site number, screening number, randomization number, gender and date of birth. Subjects will be randomized strictly sequentially within each stratum, as subjects are eligible for randomization. The RTSM will inform the investigator of the Kit ID number to be allocated to the subject at each dispensing visit via electronic data capture (EDC).

For both study parts, the primary and key secondary endpoints will be evaluated using the Full Analysis Set (FAS) based on the intention-to-treat principle.

### 3. ENDPOINTS

#### 3.1 Efficacy Endpoints

##### 3.1.1 Objective Response Rate

Objective Response Rate is a co-primary endpoint in Part 1 and a secondary endpoint in Part 2, and the Safety lead-in cohort.

ORR rate is defined as the number (%) of subjects with at least one visit response of CR or PR. Data obtained up until progression, or last evaluable assessment in the absence of progression, will be included in the assessment of ORR. This will be irrespective of whether or not subjects discontinued treatment or received a subsequent therapy prior to progression.

In all study parts, the primary assessment of ORR will be based on the full analysis set (FAS). Sensitivity analysis populations are described in Section 4.

The ORR is derived programmatically from the Best overall RECIST Response (BoR) for each subject.

Best overall RECIST Response (BoR) is calculated based on the overall visit responses from each RECIST assessment. It is the best response a subject has had following randomization and prior to RECIST progression or the last evaluable assessment in the absence of RECIST progression.

Categorization of BoR will be based on the RECIST criteria using the following response categories (listed in hierarchical order): complete response (CR), partial response (PR), stable disease (SD), progressive disease (PD) and inevaluable (NE) (CR>PR>SD>PD>NE).

Target Lesions (TL)	Non-Target Lesions (NTL)	New Lesions	Overall Response
CR	CR	NO	CR
CR	Non-CR/Non- PD	NO	PR
CR	Not evaluated	NO	PR
PR	Non- PD or not all evaluated	NO	PR

Target Lesions (TL)	Non-Target Lesions (NTL)	New Lesions	Overall Response
SD	Non- PD or not all evaluated	NO	SD
Not all evaluated	Non- PD	NO	NE
PD	ANY	YES or NO	PD
ANY	PD	YES or NO	PD
ANY	ANY	YES	PD

For the evaluation of the co-primary endpoint ORR in Part 1 of the study, all radiological data will be assessed by an Independent Central Review (ICR), and the BoR will be determined programmatically using the data provided by the ICR. For Part 2, the Safety lead-in and for the Part 1 secondary endpoint, ORR based on site assessments, BoR will be determined programmatically using data from the site assessments

For determination of a best response of SD, the earliest of the dates contributing towards a particular overall visit assessment will be used. A best response of SD cannot be assigned unless a visit response of SD has been recorded at least 6 weeks (-5 days) after randomization (day 1), i.e. at least 38 days (to allow for the assessment window). For CR/PR, the initial overall visit assessment that showed a response will use the latest of the dates contributing towards a particular overall visit assessment.

For subjects whose progression event is death, BoR will be calculated based on data up until the last evaluable RECIST assessment prior to death.

For subjects who die with no evaluable RECIST assessments, if the death occurred  $\leq$  12 weeks + 5 days after randomization, then BoR will be assigned to the progression (PD) category. For subjects who die with no evaluable RECIST assessments, if the death occurred  $>$ 12 weeks +5 days after randomization then BoR will be assigned to the inevaluable (NE) category.

Progression events that have been censored due to them being more than two missed visits after the last evaluable assessment will not contribute to the BOR derivation.

A subject will be classified as a responder if the RECIST criteria for a CR or PR are satisfied at any time following randomization, prior to RECIST progression (regardless of the number of missing visits prior to the assessment of CR or PR). In accordance with RECIST 1.1, response confirmation is not required.

For each treatment group, the objective response rate (ORR) is the number of responders divided by the number of subjects in the treatment group in the FAS analysis set. This will be irrespective of whether or not subjects discontinued treatment or received a new antitumor therapy prior to disease progression.

The NE category will be assigned in the following circumstances:

- For subjects who die with no evaluable post-baseline assessments, if the death occurred > 12 weeks + 5 days after randomization (i.e., if more than 2 assessments are missed).
  - Note: Subjects who die up to the week 12 assessment (scheduled up to 12 weeks + 5 days after randomization), with no evaluable post-baseline assessment will be classified as progressors and will be treated as progressors for the waterfall plots of the percentage change from baseline in tumor size, and the statistical analysis of tumor size (see 3.1.6 and Section 7.6)
  - For subjects with no evaluable post-baseline assessments, and for whom the date of progression (including death) is either unknown or censored due to missed assessments (see Section 3.1.2).

### 3.1.2 Progression-Free Survival

PFS is defined as the time from randomization (or starting treatment for the Safety lead-in) until the date of objective disease progression or death (by any cause in the absence of disease progression) regardless of whether the subject withdraws from randomized therapy or receives another antitumor therapy prior to disease progression. Subjects who have not experienced disease progression or died at the time of analysis will be censored at the time of the latest date of assessment from their last evaluable RECIST assessment. However, if the subject progresses or dies after 2 or more missed visits (12 weeks + 5 days maximum), the subject will be censored at the time of the latest evaluable RECIST Version 1.1 assessment.

The PFS time will always be derived based on the scan/assessment dates rather than visit dates and the following rules will be applied:

- Date of disease progression will be determined based on the **earliest** of the dates of the component that triggered the disease progression, i.e., if both the target lesions and the non-target lesions indicate disease progression but were scanned on different days, the earlier of the 2 dates would be applied.
- When censoring a subject for PFS the subject will be censored at the **latest** of the dates contributing to a particular overall visit assessment.

For Part 1, the co-primary endpoint, PFS, will be derived programmatically using data from the ICR. To support sensitivity analyses, PFS will also be derived programmatically using the site assessments of the Part 1 radiological data.

For Part 2 and the Safety lead-in, PFS will be derived programmatically using the site assessments of the radiological data.

In all study parts, the primary analysis of PFS will be assessed based on the FAS (see Section 4.2).

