- l. Biopsy will be performed during screening for those patients who did not have enough archival tumor tissue if the patient has provided the optional tumor tissue consent.
- m. Blood samples for PK analysis of varlitinib and any relevant circulating metabolites will be collected as follows:
Part 1 (All Patients):
- Cycle 1 Day 1: 5 minutes pre-dose, 1.5, 3, 5, and 8 hours post-dose. PK samples will be collected immediately after the ECG collections.
 - Cycle 1 Day 8: 20 minutes pre-dose, 1.5, 3, 5, and 8 hours post-dose. PK samples will be collected immediately after the ECG collections.
 - End of study after full drug washout: 28 days after last dose at the patient's safety follow-up visit. PK samples will be collected within 25 minutes after ECG evaluation.
- Part 2:
Sparse plasma sampling will be conducted for the population PK evaluation by using nonlinear mixed effects models on:
- Cycle 1 Day 1: 5 minutes pre-dose, 1-3 hours post-dose, 3-5 hours post-dose, and 5-8 hours post-dose
 - Cycle 2 Day 1: 20 minutes pre-dose, 1-3 hours post-dose, 3-5 hours post-dose, and 5-8 hours post-dose.
- Part 1 & Part 2: In addition, unscheduled PK samples will be collected at least 7 days following dose reduction of varlitinib at any cycle of treatment: up to 5 minutes pre-dose and 3-5 hours post-dose.
- n. Blood samples for potential retrospective analysis of potential biomarkers will be collected at baseline and Cycle 3 Day 1
- o. CT/MRI imaging of the chest, abdomen, and pelvis images to be performed every 6 weeks (± 5 days) from Cycle 1 Day 1. Brain and/or bone lesions may be scanned if applicable. Radiological assessments should continue until the patient experiences disease progression, regardless of whether the patient discontinues randomized therapy or starts a subsequent anti-cancer therapy.
- p. Baseline CT/MRI of the chest, abdomen, and pelvis images must be performed within 21 days prior to Cycle 1 Day 1, brain and/or bone lesions may be scanned if applicable. The CT/MRI image obtained as per site standard clinical practice prior to consent is acceptable for baseline image if it meets the protocol required CT/MRI image acquisition guidelines and time window.
- q. Additional weekly liver function test (AST, ALT, alkaline phosphatase, gamma glutamyl transferase, total bilirubin, direct bilirubin) will also be performed for all patients on Cycle 1 Day 8 and Cycle 1 Day 15.

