- r. No other additional study-related activities or assessments are mandated during follow-up visit; however, patient data available from the assessments done as part of their routine follow-up visits will be collected by the sponsor. If the patient needs to start a new anti-tumor treatment within 28 days post last study medication administration, the safety follow-up assessments should be performed within 1 day before the start of a new anti-tumor treatment.
- s. Disease status follow-up will be performed post EOT every 6 weeks from Cycle 1 Day 1, regardless of timing of EOT.
- t. Survival follow-up by either telephone or clinic visit will be performed every 12 weeks post EOT and PD until death to find out the survival status, new chemotherapy or biological treatments and the outcome of any ongoing adverse events.
- u. EOT assessments should be performed before the start of new anti-tumor treatment.

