8.4.2 Progression-Free Survival

Progression-free survival is a co-primary endpoint in Part 1, and is a secondary endpoint in Part 2.

Progression-free survival is defined as the time from randomization (or start of treatment in the Safety lead-in) until the date of objective disease progression or death (by any cause in the absence of disease progression) regardless of whether the patient withdraws from randomized therapy (study treatment in the Safety lead-in) or receives another antitumor therapy prior to disease progression. Patients who have not experienced disease progression or died at the time of analysis will be censored at the time of the latest date of assessment from their last evaluable RECIST assessment. However, if the patient progresses or dies after 2 or more missed visits, the patient will be censored at the time of the latest evaluable RECIST version 1.1 assessment.

The PFS time will always be derived based on the scan/assessment dates rather than visit dates and the following rules will be applied:

- Date of disease progression will be determined based on the earliest of the dates of the component that triggered the disease progression, i.e., if both the target lesions and the non-target lesions indicate disease progression but were scanned on different days, the earlier of the 2 dates would be applied.
- When censoring a patient for PFS, the patient will be censored at the latest of the dates contributing to a particular overall visit assessment.

For Part 1, the co-primary endpoint, PFS, will be derived programmatically using data from the ICR. To support sensitivity analyses, PFS will also be derived programmatically using the site assessments of the Part 1 radiological data.

For Part 2 and the Safety lead-in, PFS will be derived programmatically using the site radiological data.

Further details will be provided in the SAP.

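### SAP 3.1.2 pairs the missed-visit count with a day figure (12 weeks + 5 days) that disagrees with it, so applying the day figure could censor a PFS progression found after only one missed visit

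*SAP*

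**What the plan says.** The censoring rule for the Part 1 co-primary endpoint PFS is in SAP 3.1.2. An event is replaced by censoring at the latest evaluable RECIST assessment "if the subject progresses or dies after 2 or more missed visits (12 weeks + 5 days maximum"). The same section states that "The PFS time will always be derived based on the scan/assessment dates rather than visit dates", and that the derivation is done programmatically.

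Protocol 8.4.2 has the same rule as a count, with no number of days: "if the patient progresses or dies after 2 or more missed visits, the patient will be censored".

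The scan calendar is in the footnotes to Protocol Table 2. Imaging in Parts 1 and 2 is "to be performed every 6 weeks (± 5 days) from Cycle 1 Day 1" (footnote o). The calendar is not reset when treatment stops: "Disease status follow-up will be performed post EOT every 6 weeks from Cycle 1 Day 1, regardless of timing of EOT" (footnote s).

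SAP 3.1.1 uses the same number of days for patients who die with no evaluable post-baseline scan, but there it runs from randomization: "if the death occurred > 12 weeks + 5 days after randomization (i.e., if more than 2 assessments are missed"). Elsewhere in SAP 3.1.1 the censored events are described differently again: "Progression events that have been censored due to them being more than two missed visits after the last evaluable assessment".

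Neither document says which criterion governs when the count and the days disagree. SAP 3.1.2 also does not name the date from which its 12 weeks + 5 days runs. I read it as the last evaluable assessment, because that is the date to which the patient is censored.

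**The concern.** The day figure allows for one scan window. Between two post-baseline scans there are two: the earlier scan may be up to 5 days early and the later one up to 5 days late. PFS uses actual scan dates, so both windows enter the gap. A patient who keeps within every protocol window and misses one visit can therefore exceed the day figure without meeting the count.

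If the program tests the day figure, that patient's progression is removed and the patient is censored at a scan 90 to 94 days earlier. This shift is longer than the control median PFS assumed in SAP 6.1.2 (2.67 months, about 81 days). Duration of response (SAP 3.1.4) takes its end or censoring date from PFS, and Part 2 PFS uses the same definition, so both would carry the error.

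**Working it through.** **Inputs.** Scan interval 42 days and window ±5 days (Protocol Table 2, footnote o); fixed calendar from Cycle 1 Day 1 (footnotes o and s); 84 Part 1 PFS events, with 80% power at HR 0.58 (one-sided 5%) and at HR 0.54 (two-sided 5%) (SAP 6.1.2).

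**The plan's own figures.** 12 weeks + 5 days = 2 × 42 + 5 = 89 days. This is the latest in-window week-12 scan counted from a fixed starting day, so it reproduces with one window. With power = Φ(½√d·|ln HR| − z), 84 events give 80.3% at HR 0.58 and 80.6% at HR 0.54. Both stated powers reproduce.

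**Gap against number of missed visits.** With m missed visits, the gap between two post-baseline scans is 42(m + 1) ± 10 days. Counted from randomization it is 42(m + 1) ± 5 days, ignoring the up to 24 hours that Protocol 5.4.6 allows between randomization and first dose.

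| Missed visits | Between two post-baseline scans | From randomization |
|---|---|---|
| 0 | 32 to 52 days | 37 to 47 days |
| 1 | 74 to 94 days | 79 to 89 days |
| 2 | 116 to 136 days | 121 to 131 days |

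From randomization, 89 days is exactly the longest gap with one missed visit. Between post-baseline scans that maximum is 94 days. For progression found on a scan, any limit from 94 to 115 days separates one missed visit from two; 89 days does not.

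**Example.** Last evaluable scan at week 6 − 5 days (day 37), week 12 missed, progression on the scan at week 18 + 5 days (day 131). Gap = 131 − 37 = 94 days: one missed visit, every scan in window, and above 89.

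**Share of single-miss progressions affected.** Let a and b be the deviations of the earlier and later scan from target. The gap is 84 + b − a, which exceeds 89 when b − a ≥ 6.
- If a and b are independent and uniform on the integers −5 to 5, the count is 5 + 4 + 3 + 2 + 1 = 15 of 121 pairs, or 12.4%.
- If scan days cluster round the target (normal, truncated at ±5 days), the share is 2.3% with SD 2 days and 6.4% with SD 3 days.

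**Events affected.** The documents give no missed-visit rate, so f, the share of the 84 events found by scan after exactly one missed visit following a post-baseline scan, is an assumption. Under the uniform case, events lost = 84 × f × 15/121. Power is at HR 0.58, one-sided 5%, with no replacement events.

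| f (assumed) | Events after one missed visit | Wrongly censored | Power |
|---|---|---|---|
| 2% | 1.7 | 0.2 | 80.2% |
| 5% | 4.2 | 0.5 | 80.1% |
| 10% | 8.4 | 1.0 | 79.8% |
| 20% | 16.8 | 2.1 | 79.4% |

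With the clustered scan days, the f = 20% row falls to 16.8 × 0.023 = 0.4 up to 16.8 × 0.064 = 1.1 events.

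**The case against.** The strongest reply is that the operative words in SAP 3.1.2 are a count, that the days stand only in a parenthesis, and that Protocol 8.4.2 uses the count alone. On that reading, a patient with one missed visit keeps the event and no harm follows. This stands as far as it goes. A reader might infer that the plan does censor progressions after one missed visit. The documents do not support that; it happens only if the day figure overrides the count. But the SAP does not say that the count prevails, the derivation is programmatic, and the number of days is the part that can be coded directly. The two criteria still contradict each other in the definition of a co-primary endpoint.

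A reader might also infer that the limit should simply become 94 days throughout. That would be wrong for deaths, which are not tied to scan windows. Take a last scan at week 6 + 5 days (day 47), weeks 12 and 18 both missed (windows day 79 to 89 and day 121 to 131), and death on day 138. Two visits were missed, so the count censors, yet the gap is 138 − 47 = 91 days, and a 94-day limit would keep the event. The 94 to 115 day range holds only for progression found on a scan.

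The size is also open to challenge, and most of that challenge stands. The 12% depends on uniform scan days. It does not apply to deaths, to progression at week 12 after a missed week 6, or to progression by week 6. If PFS is exponential with the 2.67-month median, about 30% of control patients have an event by week 6. Unscheduled scans count too (SAP 7.2), so the grid of scan days is a rough model. The cut-off needs at least 84 events, so lost events would mainly delay it. Both arms share one schedule and are blinded, and nothing here shows a differential effect on the hazard ratio.

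The attrition-bias analysis in SAP 7.2.1.4 is only a partial safeguard. It restores actual event times after two or more non-evaluable assessments, which read literally leaves out an event after one. It also censors at subsequent therapy, so a difference from the primary result could not be attributed to this rule.

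**Conclusion.** The inconsistency is real: 89 days is the wrong day equivalent of the count when both bracketing scans are post-baseline, and the SAP does not say which criterion wins. Label: wrong as written, minor.

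If the day figure is applied, progressions 90 to 94 days after the last evaluable scan are wrongly censored. That is about 2% to 12% of those found after exactly one missed visit. In events it is probably under one, and at most about two of 84 if as many as 20% of events follow a single missed visit. Power falls from 80.3% to 79.4% at worst. These figures rest on an assumed missed-visit rate, on assumed scan-day distributions, and on reading the limit as running from the last evaluable scan. They do not support a claim that the PFS result would be materially biased. The reason to act is that a co-primary definition should have one rule with one meaning.

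**What to change.** In SAP 3.1.2, state that the count of missed scheduled assessments governs, as in Protocol 8.4.2. This alone removes the contradiction and needs no new number.

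If a day equivalent is kept as a programming aid, set it by case:
- progression found on a scan, with an earlier evaluable post-baseline scan: 12 weeks + 10 days between the two scans;
- no evaluable post-baseline scan: keep 12 weeks + 5 days from randomization;
- deaths: count the scheduled scan windows missed and use no single day limit from the last scan.

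In SAP 3.1.1, change the wording that requires more than two missed visits or assessments to two or more. A patient with no post-baseline scan who dies just after day 89 has missed exactly two, weeks 6 and 12, so two or more is also the wording that fits the limit used there.

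The cost is a one-line SAP edit, the aligned wording in 3.1.1 and a matching change in the derivation program, made before unblinding. No data collection or sample size changes.
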